## 8.8 End of trial

### Reporting in eCRF:

#### End-of-treatment form

An end-of-treatment form will be completed in the eCRF for all subjects who had been exposed to IMP, at the time when they have had their last administration of IMP. This form will also be completed for subjects who permanently discontinue IMP and subjects who withdraw from trial after having been exposed to IMP (see schedule of trial activities, Section 1.3 and Section 7.3 for early termination assessments).

The date and time of last administration of IMP will be recorded on the end-of-treatment form. It will also be recorded if the subject completed the treatment (i.e. did not permanently discontinue IMP prior to Week 16). If not, the primary reason for permanent discontinuation of IMP must be recorded (see Section 7.2.1).

#### End-of-trial form

An end-of-trial form must be completed in the eCRF for all subjects that have been randomized and/or exposed to treatment. The following data will be collected:

- Did the subject complete the trial (see Section 4.3)? If not, primary reason for not completing the trial will be recorded.
- Date of last contact.
- Primary reason for not completing the trial based on the following categories: Death, pregnancy, AE, lost to follow-up, lack of efficacy, randomized by mistake, withdrawal by subject, or other (if other, please specify).
- Did the subject attend the primary endpoint visit?
- Primary reason for not attending the primary endpoint visit based on the above categories.
- Did the subject attend the follow-up visit?
- Primary reason for not attending follow-up visit based on the above categories.

The end-of-trial form will be completed when the subject has had their last visit (that is, the final follow-up visit [either at Week 32 for subjects who complete the trial or earlier for subjects who permanently discontinue IMP before Week 16 or subjects who withdraw after Week 16] or the early termination visit [for subjects who withdraw from the trial before Week 16]).

THIS DOCUMENT CONTAINS CONFIDENTIAL INFORMATION AND MUST NOT BE COPIED OR MADE AVAILABLE TO ANY THIRD PARTY WITHOUT THE PRIOR WRITTEN CONSENT OF THE LEO PHARMA GROUP

## 8.9 Storage of biological samples

Primary samples (set A samples) for PK will be discarded by the bioanalytical lab upon finalization of the CTR whereas backup samples (set B samples) stored at the central laboratory will be retained no longer than 6 months after completion of the CTR.

Primary samples (set A samples) for ADA evaluation will be discarded by the bioanalytical lab upon finalization of the CTR whereas backup samples (set B samples) stored at the central laboratory will be retained for up to 10 years after final CTR, and then they will be destroyed. Any B samples that have been sent to the bioanalytical lab and used for analysis will also be discarded upon finalization of the CTR. The B samples stored at the central laboratory will be transferred to a central archive facility for long-term storage upon finalization of the CTR.

Any residual PD sample (serum and biopsy) will be stored in a biobank as described below.

### Biobank

This protocol includes the collection and analysis of biological samples. If consent is given by the subject, LEO Pharma will store residual serum and biopsy samples collected in a biobank. The biobanked biological samples will be used for future research by LEO Pharma. Donation of the samples for future research is voluntary and subjects must give their written consent to this component to confirm donation and storage and the terms associated herewith. Consent to this component will be recorded in the eCRF.

The samples will be transferred from the relevant laboratory to the biobank. The samples will be labelled with the trial ID, subject ID, and the sample date to protect the privacy of the subjects and to allow continued blinding for future analyses. The samples in this trial will be stored in the biobank for a maximum of 10 years after CTR finalization and will then be destroyed. Results of future research will be reported separately, and individual subject data will not be provided to trial sites unless requested.

THIS DOCUMENT CONTAINS CONFIDENTIAL INFORMATION AND MUST NOT BE COPIED OR MADE AVAILABLE TO ANY THIRD PARTY  
WITHOUT THE PRIOR WRITTEN CONSENT OF THE LEO PHARMA GROUP

## 9 Scientific rationale for trial design and appropriateness of assessments

### 9.1 Scientific rationale for trial design

This is a randomized, double-blind, placebo-controlled, multi-site, parallel-group, dose-finding trial, which will be conducted in accordance with the protocol, ICH GCP, and applicable regulatory requirements.

The trial will be conducted at multiple trial sites located in Europe, North America, and Japan.

Patients with AD represent a heterogeneous patient population with disease severity ranging from mild to severe. To mitigate any potential difference in trial outcome based on baseline characteristics, eligibility criteria for inclusion have been carefully selected and trial subjects will be randomized according to a stratified, permuted block design. The randomization will minimize selection bias and ensure that the effect of treatment is not confounded by baseline factors. The stratified permuted block design and the inclusion of prognostic baseline factors in the analysis will improve the precision of the estimated treatment effect.

The most important inclusion criteria for entry into the trial is a diagnosis of AD (as defined at screening by the Hanifin and Rajka 1980 criteria (62)) and history of AD for at least 1 year, to ensure correct diagnosis and rule out differential diagnoses.

Patients with moderate-to-severe AD with inadequate response to treatment with TCS ( $\pm$ TCI as appropriate), or for whom these topical AD treatments are medically inadvisable, are the target population for treatment with LEO 138559. Only adults (aged 18–75 years) are included. In order to evaluate any efficacy of LEO 138559, subjects in the trial cannot be on concomitant medication for AD or have diseases that may influence the evaluation of AD signs and symptoms.

LEO Pharma plans to evaluate LEO 138559 administered SC in 4 different dose regimens.

The following LEO 138559 dose regimens will be included:

- Dose regimen 1: LEO 138559 [REDACTED] mg SC Weeks 0, 1, 2, 3 and then [REDACTED] mg SC Q2W from Week 4.
- Dose regimen 2: LEO 138559 [REDACTED] mg SC Weeks 0, 1, 2 and then [REDACTED] mg SC Q2W from Week 4.
- Dose regimen 3: LEO 138559 [REDACTED] mg SC Weeks 0 and 2 and then [REDACTED] mg SC Q2W from Week 4.
- Dose regimen 4: LEO 138559 [REDACTED] mg SC Weeks 0 and 2 and then [REDACTED] mg SC Q2W from Week 4.

THIS DOCUMENT CONTAINS CONFIDENTIAL INFORMATION AND MUST NOT BE COPIED OR MADE AVAILABLE TO ANY THIRD PARTY WITHOUT THE PRIOR WRITTEN CONSENT OF THE LEO PHARMA GROUP

[figure not shown]
The dose regimens selected for the trial are based on the PK data from the FiH phase 1 (LP0145-1315) trial, a phase 1 (LP0145-1486) trial, and a phase 2a trial (LP0145-1376) pooled in a population PK model. The efficacy data from these trials have also been used to guide the dose selection, and the preliminary PK/PD model suggests correlation between [REDACTED], exposure, and response. Due to the limited data from the phase 2a trial, a subgroup analysis based on [REDACTED] is associated with high uncertainty, but the data suggest that [REDACTED] subjects [REDACTED] would benefit from a higher dose than in the phase 2a trial (LP0145-1376, 450 mg Q2W). No safety concern is thought to be associated with higher exposure in [REDACTED] subjects, as only mild and moderate AEs have been observed in the completed clinical trials and there was no apparent correlation between exposure and AEs. The rationale for the dose selection is also described and summarized in a separate document that also includes details of the population PK model (78).

Based on the available efficacy and safety data from completed clinical trials and in order to identify a dose which can provide maximum efficacy in this patient population, a dose regimen of [REDACTED] mg loading dose at Week 0, 1, 2, 3 (to reach steady-state concentrations faster), followed by [REDACTED] mg Q2W dosing from Week 4 onwards (dose regimen 1) is included in the planned phase 2b trial. With this dose regimen, it is predicted that maximum serum concentration ( $C_{max}$ ) will be reached by Week 4 [REDACTED]  $\mu$ g/mL in a 75-kg subject) (Panel 13). The predicted average  $C_{max}$  is below the maximum observed serum concentrations in the phase 2a trial (LP0145-1376).

THIS DOCUMENT CONTAINS CONFIDENTIAL INFORMATION AND MUST NOT BE COPIED OR MADE AVAILABLE TO ANY THIRD PARTY WITHOUT THE PRIOR WRITTEN CONSENT OF THE LEO PHARMA GROUP

**Panel 13: Simulated serum concentrations of LEO 138559 in the phase 2b trial (LP0145-2240) at a body weight of 75.0 kg**

Simulated serum concentrations for the 4 dose regimens in the phase 2b trial for a subject with a body weight of 75.0 kg. The red dashed line indicates the maximum observed concentration in the phase 2a trial (█ µg/mL).

**Abbreviations:** Q2W = every 2 weeks; W = Week.

The dosing of █ mg Q2W in dose regimen █ dose regimen used in the phase █. In the phase █ demonstrated a statistically significant difference in favor of LEO 138559 compared to placebo with regards to change in EASI score from baseline to Week 16, and it was shown to be well tolerated. With this dose regimen, steady-state concentration is predicted to be reached by Week 14 (█ µg/mL in a 75-kg subject) (Panel 13).

Dose regimens 3 and 4 have been included to provide a 2- and 4-fold lower exposure compared to the dose regimen 1, respectively. This is to provide a sufficient difference in exposure between the dose regimens to allow for a meaningful comparison of efficacy, and to secure that the dose regimens cover a sufficient exposure range to investigate a dose exposure response relationship. It will also allow for testing the impact of possible covariates, such as body weight, on the response.

A treatment duration of 16 weeks was chosen to ensure capturing a maximal effect of the active compound, LEO 138559, after exposure steady state is reached. Based on phase 2a

THIS DOCUMENT CONTAINS CONFIDENTIAL INFORMATION AND MUST NOT BE COPIED OR MADE AVAILABLE TO ANY THIRD PARTY WITHOUT THE PRIOR WRITTEN CONSENT OF THE LEO PHARMA GROUP

data, the clinical efficacy steady state for EASI-75 is anticipated to have been reached by Week █. The 18 weeks of follow-up after the last active IMP administration at Week 14 (corresponding to 16 weeks after the end of the treatment period at Week 16), is based on █ half-lives for LEO 138559 ( $t_{1/2}$  between █ days).

The trial endpoints have been selected to evaluate the efficacy of LEO 138559 in improving the severity and extent of AD. EASI and vIGA-AD will be used in this clinical trial as investigator-rated assessments of disease severity. EASI is a validated measure used in clinical practice and clinical trials to assess the severity and extent of AD (68, 79). vIGA-AD is a validated instrument used in clinical trials to assess the subject's global AD. The primary endpoint of the trial is to evaluate the percent change in EASI score from baseline to Week 16. The trial endpoints will also address subject's perception of disease severity and the impact on sleep, daily activity, and HRQoL, and safety.

## 9.2 Appropriateness of assessments

### Efficacy assessments

EASI, SCORAD, and vIGA-AD are validated measures used in clinical trials by investigators to assess the severity and/or extent of AD (see Sections 8.3.1, 8.3.2, and 8.3.3) (68-71).

### PROs

A range of validated PROs will be used to assess subject perception of AD independently of the investigator or trial staff. The PROs have been selected to assess the key signs and symptoms of AD (including itch) and HRQoL (Section 8.3.5).

### Safety assessments

Standard clinical methods of subject evaluations, such as AE monitoring (Section 10), vital signs, physical examination, ECG, laboratory testing including pregnancy testing, and ADA will be used to assess subject safety (Section 8.4). Given some large proteins may cause indirect adverse cardiac effects upon long-term exposure, data on ECG will be collected and evaluated (Section 8.4.4). Data on ADA will be collected in order to evaluate the potential immunogenicity of LEO 138559 (Section 8.4.6).

### PK assessments

Serum concentration of LEO 138559 will be measured to further characterize the PK of LEO 138559 in subjects with moderate-to-severe AD (Section 8.5). The serum concentrations will be summarized and reported in the CTR as well as subjected to population PK analysis and reported separately and may be used in an exploratory exposure-response analysis to support dose selection in future clinical trials.

THIS DOCUMENT CONTAINS CONFIDENTIAL INFORMATION AND MUST NOT BE COPIED OR MADE AVAILABLE TO ANY THIRD PARTY WITHOUT THE PRIOR WRITTEN CONSENT OF THE LEO PHARMA GROUP

## PD assessments

Biomarkers in serum will be evaluated to assess the molecular response of LEO 138559 on inflammatory processes in AD in general, and more specifically on the IL-22 pathway. The collection of skin tape strips (mandatory for subjects at selected sites) and biopsies (volunteer subjects at selected sites) permits the exploratory analysis of the effect of LEO 138559 treatment on cutaneous features of AD and in particular the IL-22 pathway. The collection of skin swabs will allow to capture the impact of LEO 138559 treatment on *S. aureus* abundance and the microbiome profile. All PD assessments aim at exploring the mechanism of LEO 138559 and to potentially identify sub-populations of AD subjects with increased response to treatment.

THIS DOCUMENT CONTAINS CONFIDENTIAL INFORMATION AND MUST NOT BE COPIED OR MADE AVAILABLE TO ANY THIRD PARTY  
WITHOUT THE PRIOR WRITTEN CONSENT OF THE LEO PHARMA GROUP

## 10 AE, SAE, and other safety reporting

AEs and SAEs are defined in Appendix 2 (Section [12.2](#)).

### 10.1 Time period and frequency of collecting AE information

All AEs will be collected from the signing of the ICF until end-of-trial (defined as the last visit in the trial), at the timepoints specified in the schedule of activities (Section [1.3](#)).

Pre-existing conditions (including those found as a result of screening procedures) will be recorded as medical history.

The timing of AE start (i.e. whether prior to or after IMP administration) will be recorded in the eCRF as described in Appendix 2 (Section [12.2.4](#)).

All SAEs will be recorded and reported to LEO Pharma immediately without undue delay but no later than within 24 hours of awareness, as indicated in Appendix 2 (Section [12.2.5](#)). The investigator will submit any updated SAE data to LEO Pharma within 24 hours of it being available.

### 10.2 Method of detection AEs

AEs must be assessed by a physician.

Care will be taken not to introduce bias when detecting AEs. Open-ended and non-leading verbal questioning of the subject is the preferred method to inquire about AE occurrence.

At all visits, the subject will be asked a non-leading question by the investigator about AEs, e.g.: "How have you felt since I saw you last?" It is important that the investigator also observes the subject for any changes not reported by the subject and records these changes.

Principles for data entry in the eCRF are described in Sections [8.4.1](#) to [8.4.5](#).

### 10.3 Follow-up of AEs and SAEs

After the initial AE/SAE report, the investigator is required to proactively follow-up with the subject at subsequent visits/contacts. All SAEs will be followed until resolution, stabilization, until the event is otherwise explained, or the subject is lost to follow-up (as defined in Section [7.5](#)). Further information on follow-up procedures is given in Appendix 2 (Section [12.2.4](#)).

THIS DOCUMENT CONTAINS CONFIDENTIAL INFORMATION AND MUST NOT BE COPIED OR MADE AVAILABLE TO ANY THIRD PARTY WITHOUT THE PRIOR WRITTEN CONSENT OF THE LEO PHARMA GROUP

## 10.4 Regulatory reporting requirements for SAE

Prompt notification (within 24 hours, see Appendix 2 [Section 12.2.5]) by the investigator to LEO Pharma of an SAE is essential so that legal obligations and ethical responsibilities towards the safety of subjects and the safety of a trial treatment under clinical investigation are met.

LEO Pharma has a legal responsibility to notify both the local regulatory authority and other regulatory agencies about the safety of a trial treatment under clinical investigation.

LEO Pharma will comply with country-specific regulatory requirements relating to safety reporting to the regulatory authority, IRB/IEC, and investigators.

An investigator who receives an investigator safety report describing an SAE or other specific safety information (e.g. summary or listing of SAEs) from LEO Pharma will review and then file it along with the investigator's brochure and will notify the IRB/IEC, if appropriate according to local requirements.

All SAEs that occur during the trial until the last safety follow-up visit, whether considered to be associated with the IMP or not, must be reported to LEO Pharma on the (paper) SAE form immediately, without undue delay and no later than within 24 hours of obtaining knowledge.

The completed SAE forms must be faxed or scanned and e-mailed to Global Safety at LEO Pharma. Contact details are given as described in Appendix 2 (Section 12.2.5).

Investigators will be notified of the evolving safety profile of the IMP on an ongoing basis.

## 10.5 Pregnancy

Details of all pregnancies will be collected after first exposure to IMP and until the subject has completed the trial. The pregnancy must be reported to LEO Pharma within 24 hours of first knowledge using the (paper) pregnancy form (part I). All pregnancies must be followed up until delivery or termination, and outcome must be reported on the (paper) pregnancy form (part II) within 24 hours of first knowledge.

The completed pregnancy forms must be faxed or scanned and e-mailed to Global Safety at LEO Pharma. Contact details are given in Appendix 2 (Section 12.2.5).

Pregnant subjects must immediately discontinue IMP permanently (Section 7.2.1).

While pregnancy itself is not considered to be an AE or SAE, any pregnancy complication or elective termination of a pregnancy for medical reasons will be reported as an AE or SAE.

THIS DOCUMENT CONTAINS CONFIDENTIAL INFORMATION AND MUST NOT BE COPIED OR MADE AVAILABLE TO ANY THIRD PARTY  
WITHOUT THE PRIOR WRITTEN CONSENT OF THE LEO PHARMA GROUP

Abnormal pregnancy outcomes (e.g. spontaneous abortion, foetal death, stillbirth, congenital anomalies, ectopic pregnancy) are considered to be SAEs and will be reported as such. For SAE definitions, see Appendix 2 (Section [12.2.2](#)).

The subject will be followed to determine the outcome of the pregnancy. The investigator will collect follow-up information on the subject and the neonate and the information will be forwarded to LEO Pharma.

Any post-trial pregnancy-related SAE considered reasonably related to the IMP by the investigator will be reported to LEO Pharma as described in Section [10.4](#). While the investigator is not obligated to actively seek this information about former trial subjects, he or she may learn of an SAE through spontaneous reporting.

## **10.6 Other events that require expedited reporting**

Not applicable.

## **10.7 Reporting of other events**

### **10.7.1 AEs of special interest**

Eczema herpeticum is considered an AESI. If available (e.g. as part of the standard clinical practice), the below additional skin findings are to be recorded in the eCRF:

- Lesion type (papules, vesicles, crusts, eroded pits, other).
- Disseminated/localized.
- Location (face, scalp, back, chest, upper limb, lower limb, genitals).
- Present in an area with visible eczema / no visible eczema / present in areas with and without eczema.
- Monomorphic/polymorphic.
- Confirmation of herpes simplex virus (not confirmed, PCR, viral culture, Tzanck, other).

### **10.7.2 Medication error**

Medication error refers to any unintentional error in the dispensing or administration of an IMP.

Medication errors include accidental overdose or underdose, inappropriate schedule of product administration, incorrect route of product administration, wrong product administered, and expired product administered.

Accidental overdose or underdose where a clinical consequence occurred or could have occurred should be recorded based on investigator judgement.

THIS DOCUMENT CONTAINS CONFIDENTIAL INFORMATION AND MUST NOT BE COPIED OR MADE AVAILABLE TO ANY THIRD PARTY WITHOUT THE PRIOR WRITTEN CONSENT OF THE LEO PHARMA GROUP

Inappropriate schedule of product administration where a clinical consequence occurred or could have occurred should be recorded based on investigator judgement. See also Section [6.8.3](#) for recording of treatment non-compliance.

Medication error must be recorded on the Other Events Involving IMP form in the eCRF. In addition, any clinical consequences of the medication error must be recorded as separate AEs on the AE form. If the AE originating from the medication error qualifies as an SAE, expedited reporting is required (Appendix 2, [Section [12.2.5](#)]).

If the medication error is due to a device deficiency, the device deficiency must be reported as a product complaint as described in Section [6.10](#).

THIS DOCUMENT CONTAINS CONFIDENTIAL INFORMATION AND MUST NOT BE COPIED OR MADE AVAILABLE TO ANY THIRD PARTY WITHOUT THE PRIOR WRITTEN CONSENT OF THE LEO PHARMA GROUP

## 11 Statistical considerations

### 11.1 Sample size

A total of 250 subjects, including at least 25 Japanese subjects will be randomized in a 1:1:1:1:1 ratio to 1 of the 5 treatment regimens outlined in Section 6.2.

The sample size is chosen, based on the results of a simulation. The simulation assessed the power to reject the null hypotheses included in the testing hierarchy specified in Section 11.3.6. Additionally, the simulation was used to discern, for which effect sizes, the trial would have approximately 50% power to detect a significant difference, in the mean percent change from baseline in EASI score at Week 16 between dose regimens 1 and 2, at the 5% significance level.

The percent change from baseline was simulated in a 4-step process. First, baseline EASI scores were obtained by resampling from a large phase 3 development program in moderate-to-severe AD. Next, the change from baseline was simulated for each subject under a multivariate normal assumption. The assumed mean change from baseline in EASI score from Week 1 to 16 was based on a component related to the effect of treatment, provided in Panel 14 for all 5 dose regimens and an effect related to the baseline EASI score for each assessment.

#### Panel 14: Assumed values for the mean change from baseline in EASI score from Week 1 to Week 16

	Wk 1	Wk 2	Wk 3	Wk 4	Wk 6	Wk 8	Wk 10	Wk 12	Wk 14	Wk 16
Dose regimen 1	-6.8	-10.3	-13.8	-17.3	-19.6	-18.8	-18.2	-17.8	-19.3	-20.7
Dose regimen 2	-5.0	-7.6	-10.2	-12.8	-14.5	-13.9	-13.5	-13.2	-14.3	-15.3
Dose regimen 3	-5.0	-6.8	-9.2	-11.5	-13.1	-12.5	-12.2	-11.9	-12.9	-13.8
Dose regimen 4	-3.3	-5.0	-6.6	-8.3	-9.4	-9.0	-8.8	-8.6	-9.3	-10.0
Placebo	-1.9	-3.8	-4.2	-4.6	-5.4	-3.8	-4.6	-5.4	-4.5	-3.5

Abbreviations: Wk = Week.

The assumptions for the placebo and dose regimen 2 groups are based on the observed data from the phase 2a proof-of-concept trial. Based on PK/PD modeling, it is anticipated that dose regimens 3 and 4 will retain approximately 90% and 65% of the mean change from baseline in EASI score observed for dose regimen █ in the phase █ trial. For dose regimen 1, the mean change from baseline in EASI score from Week 1 to Week 16 is assumed to have an additional reduction of 35% compared to dose regimen 2.

THIS DOCUMENT CONTAINS CONFIDENTIAL INFORMATION AND MUST NOT BE COPIED OR MADE AVAILABLE TO ANY THIRD PARTY WITHOUT THE PRIOR WRITTEN CONSENT OF THE LEO PHARMA GROUP

The covariance matrices for the 5 dose regimens in the simulation were assumed to be equal and have a compound symmetry structure with variances equal to 111.0 and covariances equal to 32.5.

The third step was to ensure that the underlying EASI scores from Week 1 to 16 were within the range of the EASI score scale, which runs from [0,72]. This implies natural bounds for the individual simulated changes from baseline in EASI score, as they must lie within the interval, [-baseline score, 72-baseline score].

The final step was to derive the percent change from baseline in EASI score from Week 1 to Week 16, by dividing the simulated changes in baseline in EASI score from Week 1 to 16 by the subject's baseline EASI score.

The simulation further assumed that percentage of subjects withdrawing or experiencing an intercurrent event by Week 16 in dose regimens 1-4 and placebo arms are 20%, 20%, 30%, 40%, and 40%, respectively, the timing of which was assumed to be exponentially distributed.

To approximate the power, 1,000 data sets with 250 subjects were generated based on the randomization scheme. For each data set, 100 complete versions were generated by imputing missing data separately for each treatment arm. The baseline and all post-baseline EASI assessments were included in the imputation model. The imputed data sets were analyzed based on an ANCOVA model. The pooled estimate of the difference in the LSmean change from baseline, along with the associated 95% Cis and nominal p-values, were derived for each simulated data set by applying Rubin's rules to the estimates and standard errors from the ANCOVA analysis of the imputed datasets.

**Panel 15** provides the nominal power as well as the prioritized power based on the hierarchical testing procedure, to reject the null hypotheses testing the LEO 138559 dose regimens 1-4 versus placebo, with respect to the differences in the mean percent change in EASI score from baseline to Week 16.

THIS DOCUMENT CONTAINS CONFIDENTIAL INFORMATION AND MUST NOT BE COPIED OR MADE AVAILABLE TO ANY THIRD PARTY WITHOUT THE PRIOR WRITTEN CONSENT OF THE LEO PHARMA GROUP

**Panel 15: Approximate nominal and prioritized power for rejecting the null hypotheses including in the testing hierarchy, based on the results of the simulation**

Hypothesis	Nominal power	Prioritized power
Dose regimen 1 vs Placebo	~100%	~100%
Dose regimen 2 vs Placebo	99.1%	~99.1%
Dose regimen 3 vs Placebo	97.2%	~96.4%
Dose regimen 4 vs Placebo	67.4%	~65.0%
Dose regimen 1 vs 2	49.7%	NA

**Note:** ~100% power refers to scenarios in which the associated null hypothesis was rejected in each of the 1,000 simulated trials.

**Abbreviations:** NA = not applicable.

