## 11.3 Statistical analysis

### 11.3.1 General principles

Baseline measurements are defined as the latest available observation at or prior to the date of the first IMP administration, unless otherwise specified.

All significance tests will be two-sided using the 5% significance level. All CIs will be presented with 95% degree of confidence, unless otherwise specified. LSmeans will be estimated using the observed margins for the FAS.

THIS DOCUMENT CONTAINS CONFIDENTIAL INFORMATION AND MUST NOT BE COPIED OR MADE AVAILABLE TO ANY THIRD PARTY WITHOUT THE PRIOR WRITTEN CONSENT OF THE LEO PHARMA GROUP

An observed-cases approach will be used for tabulations of data by visit (that is, involving only those subjects who attended each specific visit).

Categorical data will be summarized using the number and percentage of subjects in each category and treatment group. Continuous data will be summarized using the mean, SD, median, 1st quartile and 3rd quartile, minimum, and maximum values.

All the analyses specified in the protocol will be reviewed in relation to the blinded data actually obtained, and the SAP will be finalized before breaking the randomization code.

Any changes from the statistical analyses planned in this clinical trial protocol will be described and justified in a protocol amendment, the SAP and/or in the CTR, dependent on the type of change.

Unless otherwise stated, efficacy analyses will be performed based on the FAS, safety analyses will be based on the safety analysis set, and PK analyses will be based on the PK analysis set.

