### 11.3.6 Testing strategy

The following hierarchical procedure will be used to ensure strong control of the familywise error rate at the 5% significance level (two-sided significance tests), when testing the null hypotheses associated with the primary endpoint, percent change in EASI score from baseline to Week 16:

1. LEO 138559 [REDACTED] mg SC Weeks 0, 1, 2, 3 and then [REDACTED] mg Q2W from Week 4 (dose regimen 1) versus placebo.
2. LEO 138559 [REDACTED] mg SC Weeks 0, 1, 2 and then [REDACTED] mg Q2W from Week 4 (dose regimen 2) versus placebo.
3. LEO 138559 [REDACTED] mg SC Weeks 0 and 2 and then [REDACTED] mg Q2W from Week 4 (dose regimen 3) versus placebo.
4. LEO 138559 [REDACTED] mg SC Weeks 0 and 2 and then [REDACTED] mg Q2W from Week 4 (dose regimen 4) versus placebo.

Under the hierarchical procedure, the first null hypothesis (the difference in the mean percent change in EASI score from baseline to Week 16 between dose regimen 1 and placebo is equal to 0), is tested at the 5% significance level. If that null hypothesis is rejected, the procedure will proceed to test null hypothesis 2 at the 5% significance level. However, if the first null hypothesis cannot be rejected, the procedure stops and null hypotheses 2-4 will not be formally tested. The procedure continues in this fashion, until it either encounters a null hypothesis that cannot be rejected, or all null hypotheses have been rejected. For the purposes of the hierarchical testing procedure, the hypothesis tests will be based on the analysis of the primary estimand for the primary endpoint.

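### Panel 15's prioritized power for dose regimen 4 (about 65.0%) does not fit the hierarchy applied to the same simulated trials; with one shared placebo arm it should be about 66.7%

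*Combined protocol and SAP*

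**What the plan says.** Protocol Section 11.1 bases the sample size on a simulation of 1,000 trials of 250 subjects. "A total of 250 subjects, including at least 25 Japanese subjects will be randomized in a 1:1:1:1:1 ratio", so each regimen and placebo has 50 subjects. Panel 15 then gives nominal power and "the prioritized power based on the hierarchical testing procedure", "to reject the null hypotheses testing the LEO 138559 dose regimens 1-4 versus placebo".

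| Comparison with placebo | Nominal | Prioritized (printed with a tilde) |
|---|---|---|
| Regimen 1 | about 100% (rejected in all 1,000 trials) | 100% |
| Regimen 2 | 99.1% | 99.1% |
| Regimen 3 | 97.2% | 96.4% |
| Regimen 4 | 67.4% | 65.0% |

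Section 11.3.6 defines the procedure as a fixed sequence from regimen 1 to regimen 4, each step at the full 5% level: "If that null hypothesis is rejected, the procedure will proceed to test null hypothesis 2 at the 5% significance level". It goes on "until it either encounters a null hypothesis that cannot be rejected, or all null hypotheses have been rejected". Section 11.3.1 sets the level: "All significance tests will be two-sided using the 5% significance level". The documents do not say how the prioritized column was computed from the simulated trials, and they do not mention correlation between the tests.

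**The concern.** Under a fixed sequence, the prioritized power for regimen 4 is the probability that all four nulls are rejected. In a simulation, that is the share of trials in which this happens. The four comparisons reuse one placebo arm. If the placebo mean happens to be unusually good in a simulated trial, every regimen looks worse together. A trial that fails at regimen 2 or 3 should therefore usually fail at regimen 4 as well, and the hierarchy should cost regimen 4 very little relative to its nominal power.

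Panel 15 shows a loss of 2.4 points for the row "Dose regimen 4 vs Placebo", which is the loss that unrelated tests would produce. At stake is whether a power figure, from the simulation used to choose the sample size, describes the procedure to which it is attributed.

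**Working it through.** **Inputs.** The nominal powers 0.991, 0.972 and 0.674 for regimens 2 to 4, the prioritized powers 96.4% and 65.0%, and the 1,000 trials come from Section 11.1 and Panel 15. Regimen 1 rejects in every simulated trial, so it drops out of the joint calculation. Section 11.1 also gives 50 subjects per arm and 20%, 20%, 30%, 40% (regimens 1 to 4) and 40% (placebo) withdrawing or having an intercurrent event by Week 16.

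**Step 1: what reproduces the printed figures.** Multiplying nominal powers, as if the tests were independent:
- Regimen 3: 0.991 × 0.972 = 0.9633, or 96.3% (printed 96.4%).
- Regimen 4: 0.991 × 0.972 × 0.674 = 0.6492, or 64.9% (printed 65.0%).
- Regimen 4, starting from the panel's own 96.4%: 0.964 × 0.674 = 0.6497, or 65.0%.

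**Step 2: correlation from the shared placebo arm.** With effective sizes n₀ (placebo), nᵢ and nⱼ, and equal variances, which Section 11.1 assumes for the five arms,

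ρᵢⱼ = (1/n₀) / √[(1/n₀ + 1/nᵢ)(1/n₀ + 1/nⱼ)].

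With all 50 subjects per arm, ρ = 0.50. With completers only (placebo 30, regimen 2: 40, regimen 3: 35, regimen 4: 30):
- ρ₂₃ = 0.555
- ρ₂₄ = 0.535
- ρ₃₄ = 0.519

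Pairs that include regimen 1 (40 completers) run from 0.53 to 0.57.

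**Step 3: joint power.** The test statistics are treated as multivariate normal, with margins fixed at the stated nominal powers. The joint rejection probability is then Φ(z₀.₉₉₁, z₀.₉₇₂, z₀.₆₇₄; ρ), where z are the normal quantiles of the nominal powers.

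| ρ | Regimen 3, hierarchical | Regimen 4, hierarchical | Expected trials per 1,000 rejecting regimen 4 after an earlier failure |
|---|---|---|---|
| 0 | 96.3% | 64.9% | 24.8 |
| 0.3 | 96.4% | 66.0% | 14.2 |
| 0.5 | 96.5% | 66.7% | 7.3 |
| completers (0.52 to 0.55) | 96.6% | 66.7% | 6.5 |
| 0.6 | 96.6% | 67.0% | 4.3 |

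**Step 4: the same comparison as counts.** With 1,000 trials, 0.1 point is one trial.
- Nominal minus prioritized for regimen 4 is 674 − 650 = 24 trials that reject regimen 4 after an earlier test failed.
- Trials failing earlier number 1,000 − 964 = 36.
- 24/36 = 67%, the same as the unconditional rate of 67.4%.
- Expected share under the shared placebo arm: 21% at ρ = 0.5, 19% with the completer correlations, 13% at ρ = 0.6.
- With 6.5 expected, the binomial probability of 24 or more in 1,000 is about 1 × 10⁻⁷. At ρ = 0.3 it is still only about 0.01.

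For regimen 3 the same count is 972 − 964 = 8 trials, against 6.2 expected with the completer correlations (97.2% − 96.58%). That is within simulation error.

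**Step 5: check on the dependence.** Full simulations used the Panel 14 means, the stated covariance, the score bounds, the stated missingness, arm-wise multiple imputation, ANCOVA and Rubin's rules. The baseline EASI distribution had to be assumed (mean 30 to 33, SD 12 to 13). Nominal power for regimen 4 came out lower than printed (46 to 52%), so these runs bear only on dependence. The hierarchy cost regimen 4 between 1.0 and 2.0 points, while the product of nominal powers fell 4.7 to 7.2 points short of nominal. Between 10% and 17% of trials that failed earlier rejected regimen 4.

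**The case against.** The product does not reproduce the printed figures exactly. It gives 96.3% and 64.9%, while the panel prints 96.4% and 65.0%; 65.0% appears only when the panel's own 96.4% is carried forward. A reader might infer that the authors multiplied nominal powers. The documents do not establish that: they attribute the column to the simulation without giving the derivation, and a coding or transcription slip would look the same. This objection stands, and the cause should be treated as an inference.

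Every prioritized entry carries a tilde, and the panel calls its values approximate, so reading 65.0% as exactly 650 trials may be too literal. A proportion near 65% from 1,000 trials also has a standard error of about 1.5 points (√(0.65 × 0.35/1,000) = 0.015). Neither point removes the discrepancy. Both columns are described as coming from the same trials, so the counts are nested and the relevant error is that of the discordant trials, not of a single proportion. If the tilde allowed only 19 discordant trials (prioritized power 65.5%), the probability with 6.5 expected would still be about 5 × 10⁻⁵.

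A replacement value computed outside the sponsor's simulation is less secure than a recount, because the phase 3 baseline data and the exact imputation model are not given. That also stands. The 66.7% is what to expect from the recount and should not be printed in its place.

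Finally, nothing in the design depends on 65% or 67%: Section 11.1 sets no power target for regimen 4. This is correct and limits the weight of the point.

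**Conclusion.** The prioritized power printed for regimen 4 is not consistent with the fixed-sequence procedure of Section 11.3.6 applied to the same 1,000 simulated trials. With the stated nominal powers and one shared placebo arm it should be about 66.7%, and 66.7 to 67.0% for correlations of 0.5 to 0.6. It cannot exceed the nominal 67.4%. The printed value is about 1.7 points too low, so the error is conservative. Reaching 65.0% would need a correlation of roughly 0 to 0.1, which a shared placebo arm of similar size does not give.

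This rests on the printed nominal powers being right, on approximate normality of the test statistics, and on correlations derived from the stated arm sizes and missingness.

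A reader might go further and conclude that the whole prioritized column is wrong or that the trial is wrongly sized. The figures do not support either: the regimen 3 entry is within simulation error, and the sample size, control of the familywise error rate and nominal powers are unaffected. Confidence is high in the discrepancy and limited as to its cause.

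**What to change.** Recount the prioritized column from the existing simulation output, as the share of the 1,000 trials in which the current null and all earlier nulls are rejected. Restate the regimen 4 entry with that count, expected at about 66.7%. If the column turns out to be a product of nominal powers and is kept, label it so in Panel 15, state that independence was assumed, and do not describe it as the power of the hierarchical procedure.

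The cost is a recount of stored results and one table entry, or one sentence of labelling. No new simulation, change of sample size or change to the testing strategy is needed.
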